- a) Primary Outcome
 - a) Outcome Measure Title: Reduction in severity of CINV
 - b) Outcome Measure Description: Assessed by the mean score of the Antiemesis (MAT) tool, which measures acute and delayed CINV across patients' chemotherapy regimens.
 - c) **Outcome Measure Timeframe**: Data tool collected during study visits 1, 2, 3, and 4.
- b) Secondary Outcome
 - a) Outcome Measure Title: Reduction in Antiemetic Use
 - b) **Outcome Measure Description**: Assessed by the mean score of antiemetics diary, which measures the usage frequency (date and time) and type (name) of antiemetic medications.
 - c) **Outcome Measure Timeframe**: Data diary collected during study visits 1, 2, 3, and 4.
- c) Exploratory Outcome
 - a) Outcome Measure Title: Improved Resilience
 - b) **Outcome Measure Description**: Assessed by the mean score of the Connor-Davidson Resilience Scale (CD-RISC), which measures the participants' resilience pre and post the intervention.
 - c) Outcome Measure Timeframe: Data collected at baseline and final visit.
- d) Exploratory Outcome
 - a) Outcome Measure Title: Reduction in Psychological Distress Symptoms
 - b) **Outcome Measure Description**: Assessed by the mean score of the psychological distress symptoms visual analog scale the patients' anxiety, stress, and depression at pre-and post-assessment.
 - c) Outcome Measure Timeframe: Data collected at baseline and final visit.
- e) Exploratory Outcome
 - a) Outcome Measure Title: Improved Quality of Life
 - b) **Outcome Measure Description**: Assessed by the mean score of Functional Assessment of Chronic Illness Therapy General (FACIT-G), which measures the

patients' quality of life and well-being at pre-and post-assessment.

c) Outcome Measure Timeframe: Data collected at baseline and final visit.

The study objectives and endpoints were selected because (a) more research is necessary to understand the effects of aromatherapy on moderate and high emetogenic chemotherapy regimens in an outpatient setting; (b) the literature suggests that CINV has a relationship with decreased quality of life and increased antiemetic usage and psychological distress symptoms; (c) the relationship between CINV and resilience has not been established. However, literature has shown a relationship between resilience and a reduction in psychological distress symptoms and improved quality of life.

9) Procedures Involved*

The study will continue as follows:

Initial visit

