Additionally, there is a space to name other complementary methods used to relieve CINV and describe how the CINV was controlled in the antiemetic/aromatherapy diary.

MAT Tool:

The Antiemesis (MAT) tool created by the Multinational Association of Supportive Care in Cancer (Dranisaris et al., 2017) is a user-friendly and reliable tool designed to measure acute and delayed CINV across patients entire chemotherapy regimen. The MAT tool is available in English and Spanish languages. The MAT tool consists of eight items that assess participants' CINV (i.e., occurrence, duration, and frequency). Four items assess the participants' acute phase (i.e., first 24 hours after receiving chemotherapy), and the last four items assess the delayed phase (i.e., day 2 to day 4 after chemotherapy treatment). The MAT tool has been used as a communication tool to facilitate discussions about their CINV to their healthcare providers (Alafafsheh & Ahmad, 2016; Molassiotis et al., 2007; Yamaguchi et al., 2009). This MAT tool has shown good reliability and validity, with Cronbach alpha of 0.77-0.97 in 1200 patients with cancer (Alafafsheh & Ahmad, 2016; Dranisaris et al., 2017; Molassiotis et al., 2007; Yamaguchi et al., 2009).

Antiemetic Diary (Arm 1 - Control Only):

The antiemetic diary allows the participants to record their usage (date and time) and type (name) of antiemetic medications. Additionally, there is a space to name other

complementary methods used to relieve CINV and describe how the CINV was controlled in the antiemetic diary.

Resilience Scale:

The Connor-Davidson Resilience Scale (CD-RISC) will assess the participants' resilience pre and post the intervention (Burns & Anstey, 2010). For this study, we will use the 10-item questionnaire that includes questions such as: are you 'able to adapt to change,' 'can (you) deal with whatever comes,' to 'can handle unpleasant feelings.' This scale has shown good reliability and validity, with Cronbach alpha of 0.88 in 343 patients with cancer and 122 breast patients with cancer (Matzka, Mayer, Köck-Hódi, Moses-Passini, Dubey, Jahn, ... & Eicher, 2016; Scali, Gandubert, Ritchie, Soulier, Ancelin, Chaudieu, & Uddin, 2012).

Psychological Distress Symptoms:

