All endpoints will be evaluated using parametric analysis to examine the difference between the two conditions across the 3-time points for primary endpoints (CINV and Use of Antiemetics) and 2-time points for secondary endpoints (resilience, psychological distress, and quality of life). The analysis will be conducted using SPSS Version 26. For binary outcomes (CINV), logistic regression will be used. For continuous outcomes (antiemetic use, resilience, psychological distress, and quality of life) a Mixed ANOVA will be used with condition as the between-subjects variable and change over time on the outcome as the within-subjects variable. Sphericity and homogeneity of variance assumptions will be tested prior to interpretation of the results, and the

Greenhouse-Geisser correction will be implemented if Sphericity is violated. A type I error rate of .05 will be used to determine significance for all analyses.

Outcome	Measure	Type of measurement
CINV	MAT	Binary
Use of antiemetics	Antiemetic Diary	Continuous
Resilience	CD-RISC	Continuous
Psychological Distress	Visual Analog Scale	Continuous
Quality of Life	FACIT-G	Continuous

2. Analysis of the Primary Endpoint(s)

For CINV, logistic regression will be used to determine whether the use of aromatherapy decreases the risk for any of the following outcomes: acute nausea, delayed nausea, acute vomiting, or delated vomiting. For use of antiemetic medication, a Mixed ANOVA will be used to evaluate differences between conditions (aromatherapy group vs. treatment as usual) across the 3-time points (Visit 1, Visit 2, and Visit 3). Time x treatment effects will be evaluated as well as main effects.

3. Analysis of the Secondary Endpoint(s)

For resilience, psychological distress, and quality of life, a Mixed ANOVA will be used to evaluate differences between conditions (aromatherapy group vs. treatment as usual) across the 2-time points (Initial visit and final visit). Time x treatment effects will be evaluated as well as main effects

4. Baseline Descriptive Statistics

Participant demographic characteristics will be analyzed using descriptive statistics. Specifically, frequencies and percentages will be reported for categorical variables, and means and standard deviations will be reported for continuous variables.

12) **Provisions to Monitor the Data to Ensure the Safety of Subjects***

This section is not applicable. The risks of this study are minimal.

13) Withdrawal of Subjects*

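### The primary outcome is called severity and defined by an unspecified MAT mean score, but the described MAT content has no severity item and the planned analysis tests yes/no occurrence.

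*Combined protocol and SAP*

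**What the plan says.** Three places define the primary outcome.

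- **Study Endpoints, Primary Outcome.** The title reads "Outcome Measure Title: Reduction in severity of CINV". The description reads "Assessed by the mean score of the Antiemesis (MAT) tool, which measures acute and delayed CINV".
- **Section 9, MAT Tool.** The instrument is summarised as follows: "The MAT tool consists of eight items that assess participants' CINV (i.e., occurrence, duration, and frequency". Half of these cover the acute phase, meaning the 24 hours following an infusion. For the other half it says "the last four items assess the delayed phase (i.e., day 2 to day 4 after chemotherapy treatment". It gives no response scales, score range or rule for combining items.
- **Section 11, General Approach and Analysis of the Primary Endpoint(s).** "For binary outcomes (CINV), logistic regression will be used". The accompanying table lists the MAT as binary. The regression addresses the risk of any of four outcomes: acute nausea, delayed nausea, acute vomiting and delayed vomiting. CINV is not among the outcomes assigned to the mixed ANOVA. A type I error rate of .05 applies to every analysis.

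**The concern.** Title, metric and analysis describe three different quantities: how bad the symptoms are, a numeric score with no stated construction, and whether a symptom happened at all. A sponsor following section 11 exactly would never compute the quantity defined in Study Endpoints. A sponsor following Study Endpoints would have to devise the scoring, and nothing prespecified would limit that choice.

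The difference matters for this intervention. The hypothesis under Aim 1 in section 3 concerns discomfort from CINV. Section 5 enrols only patients who already had nausea or vomiting after their first infusion. Section 9 has the inhaler used at the first sign of CINV, so symptoms will often have begun before the first inhalation. A benefit could then show up as milder or shorter nausea more than as absence of nausea. A yes/no analysis would miss that benefit, and a positive yes/no result would still not show reduced severity.

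**Working it through.** **1. Compare the three definitions.**

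| Element | Study Endpoints | Section 9, MAT Tool | Section 11 |
|---|---|---|---|
| Concept | Severity | Occurrence, duration, frequency | Occurrence |
| Metric | Mean score, no scoring rule | Eight items, four per phase; scales not given | Binary, four outcomes |
| Analysis | None given | Not applicable | Logistic regression |
| Single primary measure | One undefined score | Not applicable | None chosen among four |

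Severity appears only in the first column. The mean score has no matching analysis in the last column. The four binary outcomes in section 11 are not mentioned in the primary outcome definition.

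**2. Can the mean score be recovered from the documents?** No. It could be an average over the eight items, or an arm mean of a total, a subscale or a single item. The documents do not say which.

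**3. Does the choice matter?** It would if unlike items were averaged. Take two hypothetical patients and assume that each phase has two occurrence items, one duration item and one frequency item. In each phase both patients answer yes (1) to the two occurrence items. Patient A has duration 6 hours and frequency 1. Patient B has duration 2 hours and frequency 4. The eight-item mean is 2 × (sum for one phase) / 8.

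- Duration in hours: A = 2 × (1 + 1 + 6 + 1)/8 = 2.25; B = 2 × (1 + 1 + 2 + 4)/8 = 2.00.
- Duration in days: A = 2 × (1 + 1 + 6/24 + 1)/8 = 0.81; B = 2 × (1 + 1 + 2/24 + 4)/8 = 1.52.

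The order reverses with the unit. This shows why a scoring rule is needed. It does not show that the sponsor intends this average.

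**4. Error rate if the four binary outcomes are tested separately at .05.** The chance of at least one false positive is 1 − 0.95^4 = 0.185 under independence. Under any dependence it lies between 0.05 (identical outcomes) and 4 × 0.05 = 0.20. The four outcomes are likely to be correlated, so 0.185 is a reference value and not an estimate.

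**5. A mean and a binary outcome are different designs.** Section 6 gives N = 100 without an effect size, SD, event rate or power, so there is no plan figure to reproduce. For context, assume 50 per arm, two-sided .05, 80% power, no dropout, one measurement per patient and normal approximations.

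- Mean outcome: detectable difference = (1.960 + 0.842) × √(2/50) = 0.56 SD.
- Binary outcome, with control rates spanning the 40% and 71% quoted in section 4: the intervention rate must fall from 40% to 15.2%, 50% to 23.3%, 60% to 32.3%, or 71% to 43.6%. These are risk differences of 0.25 to 0.28.

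The documents justify N = 100 for neither.

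**The case against.** The strongest reply is that section 11 governs the analysis and is already sensible. It treats the MAT as binary, and it keeps nausea apart from vomiting and the acute apart from the delayed phase. On that view the mean-score wording is boilerplate, since the same phrase is used for the antiemetic diary, the CD-RISC, the visual analog scales and the FACIT-G. The diary has no item scale to average, so the phrase may mean no more than an arm mean.

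Much of this stands. A reader might infer that the primary outcome is an average of all eight MAT items and that its wide-range items would swamp any change in occurrence. The documents do not support that. They never say that items are averaged, and section 11 plans no such analysis. A calculation of lost power on that basis would have to treat the items as independent and hold duration and counts fixed while occurrence falls. Section 9 reports a Cronbach alpha of 0.77 to 0.97, which independent items would not give. A patient without symptoms also has no duration and no episodes.

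A reader might also infer that the MAT has no severity item. Section 9 only summarises the form, which is not reproduced, so this cannot be settled here.

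The reply does not remove the conflict. If section 11 governs, the primary outcome is occurrence, its title is wrong, its stated metric is never analysed, and four outcomes share the primary role.

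**Conclusion.** Wrong as written. The stated primary metric has no scoring rule and no planned analysis, and the planned analysis measures occurrence, so it cannot support a claim that severity was reduced. This follows from comparing the sections and needs no numerical assumption.

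No bias or power loss can be attached to it, because the documents give no MAT scale, SD or event rate. The only figure that bears on the plan as it stands is the false-positive rate of 5% to 20% across four outcomes. That figure assumes that they are tested separately at .05; section 11 does not say whether they might instead be combined into one any-of-four outcome.

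**What to change.** - **Study Endpoints:** delete the mean-score wording. Define the primary outcome by one named MAT item, in one phase, on that item's own scale. Keep nausea and vomiting and the acute and delayed phases apart, as section 11 already does. List the remaining items as secondary.
- **Title:** check the MAT form. If it holds a nausea-intensity item, use that item for severity and move it to a numeric analysis in section 11. If it does not, retitle the outcome to occurrence (or to duration or frequency), whichever is chosen.
- **Section 9, MAT Tool:** state the response scale of each item used, so that the description agrees with the endpoint.
- **Section 11:** make the measurement-type table and the primary analysis refer to that one item, and say that the other three outcomes are secondary.

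The cost is wording in the endpoint and analysis sections, with no new data. The downside is that the sponsor must commit to one item and one phase as primary, and a benefit confined to another item or phase would then count only as secondary evidence.

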The study's initial visit will occur while patients are in the CTU or fast-track area as they get ready for treatment. The entire study will be explained to the patient when they are preparing for their chemotherapy regimen in a comfortable area provided by the SCCC. After answering the potential participants' questions, the study team member will go through the study's informed consent process if the participant is interested and willing to consent. The potential participants will have time to review and discuss informed consent. After the patient signs the informed consent, the participant will be randomized to the control or the intervention arm.

On the same day, the study team member will meet the participant in the CTU while they receive their infusion and provide both the control and intervention groups, access to complete, via iPad or laptop, the electronic pre-assessment and demographic form, psychological distress VAS, resilience scale, FACIT-G, and a study packet that includes the Antiemesis (MAT) tool, antiemetic diary or antiemetic/aromatherapy diary. The study packet will be completed and returned to the study team member on the participants' next scheduled chemotherapy infusion. The study team member will explain to the participants how to use the MAT tool and how to fill the antiemetic diary or antiemetic/aromatherapy diary. The study team member will go through the instructions to ensure that they understand the forms and how to complete them.

Arm 1 - Control group:

Participants in the control group will receive standard medical care, consisting of antiemetic medicine at the first sign of CINV on a schedule as prescribed by the healthcare provider. The study team member will review with the participant how to use the weekly study packet (e.g., MAT tool and antiemetic diary) and explain that a study team member will collect the packet on their next scheduled chemotherapy infusion.

Arm 2 - Intervention group:

Participants in the intervention group will receive an aromatherapy inhaler for complementary use with their antiemetic medication. Participants will be encouraged to use the aromatherapy inhaler at the first sign of CINV before taking their antiemetic medications that are labeled "as needed". The interventional group will be instructed that one normal inhale is equivalent to one dose of aromatherapy and must report essential oils sensitivity to a study team

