A study team member and participant will meet during the participant's scheduled CTU appointment to collect their MAT tool and antiemetic/aromatherapy diary. During this interaction, the study team member will reinforce instructions and answer any participant's questions, concerns, or confusion regarding the aromatherapy inhaler, MAT tool, and antiemetic/aromatherapy diary. A new study packet and an aromatherapy inhaler, if necessary, will be provided to the participants.

Visit 3: Participants' visit three will take part on their next scheduled chemotherapy infusion – i.e., the participants' third chemotherapy cycle during their study period. A study team member

will give the participant access to complete the following assessments via iPad or laptop: postassessment and demographic form, psychological distress VAS, resilience scale, and FACIT-G.

Arm 1 - Control group:

A study team member and participant will meet during the participants' scheduled CTU appointment to collect their final MAT tool and antiemetic diary. During this interaction, the study team member will assess the participant's study experience and provide the participant with a thank you card appreciation for their study participation.

Arm 2 - Interventional group:

A study team member and participant will meet during the participants' scheduled CTU appointment to collect their final MAT tool and antiemetic/aromatherapy diary. During this interaction, the study team member will assess the participant's study experience and provide the participant with a thank you card appreciation for their study participation.

If a participant is admitted to an SCCC's inpatient unit or has their chemotherapy temporally held during their study period, the study procedures will be postponed until their next regularly scheduled outpatient CTU visit. Participants' known admissions will be noted in the respective participant's study notes.

Table 2

Timepoints	1	2	3	4
Visits	Initial	1	2	3 (Final)
Assessments collected on:				
Demographic	X*			
Pre-assessment	X*			
Psychological distress symptoms (VAS)	X*			X*
Resilience	X*			X*
FACIT-G	X*			X*
MAT tool		Х	Х	Х
Antiemetic diary		Х	Х	Х
Antiemetic/Aromatherapy diary (intervention group only)		Х	Х	Х
Post-assessment				X*

Participant's Study Period and Associated Assessments

Note: (*) indicates measures where data are entered directly in REDCap.

Interventions and Assessment Instruments:

Pre-Assessment and Demographic Checklist:

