When required to transport data or bio-specimens for this research, the research team will transport the data and bio-specimens in a de-identified (or anonymous) manner with a link to the individual subject's identity maintain separately from the data and/or bio-specimen.

26) **Provisions to Protect the Privacy Interests of Subjects**

The study team member will take steps to ensure that the participants' privacy is protected. The study team member will introduce, explain, and answer any questions

related to the study. The study team member will explain that medical information will be de-identified for the study. All participant demographic information and collected data will be encoded for confidentiality in REDCap. Participants will be assigned a number that will be utilized to track their data throughout the study. No participant personal identifying information will be utilized to share data among personnel or to analyze results from assessments. The PI and Co-PI will be responsible for assigning participant codes for data tracking and randomization. This will be done utilizing an online pseudo-random number randomizer (https://www.randomizer.org/) (Urbaniak & Plaus, 2013).

27) Compensation for Research-Related Injury

This section is not applicable. The risks of this study are minimal.

28) Economic Burden to Subjects

This section is not applicable. There is no cost to the participants.

29) **Consent Process**

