All participants are required to provide informed consent before the beginning of study procedures. The informed consent will occur at the SCCC's outpatient CTU on the patients' chemotherapy infusion visit in their quiet, comfortable setting. The consent, all study procedures, and materials will be available and completed in the participant's preferred language (English or Spanish) by a study team member fluent in the preferred language (English or Spanish). Potential participants will receive a full explanation of the study, including the study's purpose, procedure, and risks/benefits. The study team member will also explain that participation is voluntary at no cost; all study information is kept confidential, and that they may withdraw from the project without penalty or any monetary loss. Potential participants will have ample time to ask any pertinent questions related to the study. After answering all their questions, and the potential participant understands the study information, a study team member will go through the informed consent process in the participant's preferred language. The study team member will allow the participant to decide whether they want to participate. Once the informed consent is signed in REDCap, a copy will be provided to the participant, the signed consent will be uploaded to the participant's electronic medical record, and sent via encrypted email to the treating oncologist notifying them of the patient's consent to participate in the study. The study team member will provide the study's contact information should the participant have any additional questions during the study.

Non-English-Speaking Subjects

The consent, all study procedures, and materials will be available and completed in the participant's preferred language (English or Spanish) by a study team member fluent in the preferred language (English or Spanish).

30) **Process to Document Consent in Writing**

All recruited participants will sign the informed consent before receiving the study's instructions, assessments, and packet. The consent and data will be stored in the password-protected University of Miami's secure server, REDCap.

Type of Request:

- Waiver of Authorization for access to medical record for subject identification/recruitment.
 - Waiver of Authorization for access to medical record to obtain data for the research.

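### Baseline distress, resilience and quality-of-life scores are taken after randomisation with no masking described, and the planned two-time-point Mixed ANOVA uses them less efficiently than ANCOVA

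*Combined protocol and SAP*

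**What the plan says.** **Order of events.** Section 9 (Initial visit) puts allocation directly after consent: "After the patient signs the informed consent, the participant will be randomized to the control or the intervention arm". The next paragraph has a team member meet the participant during the infusion that day. Both groups then receive several items, among them: "psychological distress VAS, resilience scale, FACIT-G, and a study packet that includes the Antiemesis (MAT) tool, antiemetic diary or antiemetic/aromatherapy diary". The diary differs by arm. The inhaler and the arm-specific instructions are described under the same visit.

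**Masking.** The control arm receives standard care with no sham inhaler. Section 26 on privacy says who allocates, "The PI and Co-PI will be responsible for assigning participant codes for data tracking and randomization", and names an online randomiser. It says nothing about when the participant learns the arm. Section 30 requires only that consent come first: "All recruited participants will sign the informed consent before receiving the study's instructions, assessments, and packet". Table 2 lists the scales at the initial visit without ordering them against randomisation; its note on the starred measures, which include all three scales, "indicates measures where data are entered directly in REDCap".

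**Analysis.** Section 11, General Approach, gives "2-time points for secondary endpoints (resilience, psychological distress, and quality of life". Section 11, item 3 says: "For resilience, psychological distress, and quality of life, a Mixed ANOVA will be used to evaluate differences between conditions", across the initial and final visits, and adds: "Time x treatment effects will be evaluated as well as main effects". There is no baseline covariate. An earlier paragraph of section 11 also plans paired t-tests or Wilcoxon signed-rank tests for pre- and post-assessments, without saying whether these three scales are included.

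**The concern.** There are two separate points.

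**Timing.** A baseline should be fixed before anything about the allocation can affect it. Here the patient has had the whole study explained and been randomised, and then rates anxiety, stress, depression, resilience and well-being. Someone pleased or disappointed with the allocation may answer differently. The planned analysis subtracts that answer from the final score, so a difference created at baseline can appear as a treatment effect or hide one.

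**Efficiency.** With two time points the Mixed ANOVA interaction is a comparison of change scores. It is a valid test when the baseline is unaffected by arm, but it discards precision that ANCOVA recovers from the same data. The plan also lists main effects without saying that the condition main effect, which averages the baseline with the final score, is not the efficacy test.

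The reach is limited to resilience, distress and quality of life, which are exploratory in the Study Endpoints list and secondary in section 11.

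**Working it through.** **Inputs from the documents.** Total N is 100 (section 6); the type I error rate is 0.05 and the model is a two-time-point Mixed ANOVA (section 11). No effect size, SD, power, dropout, allocation ratio or pre-post correlation is given, so N = 100 cannot be reproduced.

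**Assumptions.** 1:1 allocation, n = 50 per arm unless stated, SD 1 at both times, two-sided 0.05, normal approximation. The pre-post correlation ρ is varied.

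**Step 1: what the planned test is.** With two time points the time × treatment F equals the square of the change-score t. A numerical check on simulated data gave F = t² = 11.344.

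**Step 2: efficiency with a clean baseline.**
- Var(change-score difference) = 2(1−ρ) × 2/n
- Var(ANCOVA difference) = (1−ρ²) × 2/n
- Ratio ANCOVA/change = (1+ρ)/2, below 1 for every ρ < 1
- Condition main effect: estimates half the final-visit effect, with variance ((1+ρ)/2) × 2/n

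Example at ρ = 0.5: SE(change) = √(2 × 0.5 × 0.04) = 0.200; SE(ANCOVA) = √(0.75 × 0.04) = 0.173.

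| ρ | Variance ratio | Power at 0.5 SD: change / ANCOVA / main effect | Power at 0.3 SD: change / ANCOVA | Power at 0.5 SD, 40 per arm: change / ANCOVA |
|---|---|---|---|---|
| 0.3 | 0.65 | 56.1% / 74.6% / 34.1% | 24.5% / 34.9% | 47.2% / 65.0% |
| 0.5 | 0.75 | 70.5% / 82.3% / 30.3% | 32.3% / 41.0% | 60.9% / 73.3% |
| 0.7 | 0.85 | 89.8% / 93.8% / 27.3% | 49.1% / 55.6% | 82.3% / 87.9% |
| 0.8 | 0.90 | 97.7% / 98.6% / 26.1% | 66.0% / 70.5% | 94.2% / 96.1% |

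The last column represents an assumed 20% dropout. Simulated power at 0.5 SD and 50 per arm agrees to within about 2 percentage points.

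**Step 3: a baseline shifted by knowledge of the arm.** Let knowing the arm move one arm's baseline by d, and let a fraction k of that shift remain in the final score. Then:
- bias of the change score = (k−1)d
- bias of ANCOVA = (k−ρ)d
- the two are equal in size at k = (1+ρ)/2; ANCOVA has the smaller bias below that value and the larger bias above it.

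Rejection rates with no true effect (change score / ANCOVA):

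| d | k | ρ = 0.3 | ρ = 0.5 | ρ = 0.7 |
|---|---|---|---|---|
| 0.1 | 0 | 7.1% / 5.3% | 7.9% / 6.0% | 9.9% / 7.8% |
| 0.1 | 1 | 5.0% / 6.6% | 5.0% / 6.0% | 5.0% / 5.5% |
| 0.2 | 0 | 13.5% / 6.1% | 17.0% / 8.9% | 25.2% / 16.5% |
| 0.2 | 0.5 | 7.1% / 5.5% | 7.9% / 5.0% | 9.9% / 5.9% |
| 0.2 | 1 | 5.0% / 11.4% | 5.0% / 8.9% | 5.0% / 7.0% |
| 0.3 | 0 | 24.5% / 7.6% | 32.3% / 13.9% | 49.1% / 31.2% |
| 0.3 | 1 | 5.0% / 19.6% | 5.0% / 13.9% | 5.0% / 9.7% |

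Simulation at d = 0.2, ρ = 0.5 (8,000 trials per cell) agrees: 16.8% / 8.7% at k = 0 and 5.2% / 8.1% at k = 1. With d = 0 there is no bias.

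**The case against.** **The harm is inferred.** The protocol says when participants are randomised, not when they are told. In section 9 the questionnaires are listed before the packet, and the inhaler is described later, so disclosure after the scales is possible. The VAS asks about the past 7 days, which limits its sensitivity to news received that day. This stands: the right claim is exposure to influence, not demonstrated bias, and every rejection rate in step 3 is a scenario.

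**A clean baseline may not make the comparison cleaner.** The final self-reports remain open-label. If the final-visit shift kd comes from knowing the arm at that time, it survives the reordering. Bias then becomes kd for both analyses. At d = 0.2, ρ = 0.5 and k = 1, rejection would be 5.0% as planned, but 17.0% (change score) or 21.1% (ANCOVA) with a clean baseline; at k = 0 the planned test would fall from 17.0% to 5.0%. If the final shift is only carry-over from the baseline answer, reordering removes it. This also stands. Earlier completion protects the baseline scores; it does not remove open-label reporting at the end. A design in which one unmeasured bias might cancel another is still no reason to leave the baseline exposed.

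**ANCOVA is a preference and can be worse.** The planned interaction is valid with a clean baseline, the gain at 0.5 SD is only 4 percentage points at ρ = 0.7 and about 1 at 0.8, and ANCOVA is the more biased of the two when a shift persists. That is correct, and it is why ANCOVA is recommended for precision only.

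**Reach and cost.** The scales are exploratory or secondary. The statement that CINV and antiemetic use are untouched rests on Table 2 and section 11; the Study Endpoints list gives visits 1 to 4, which does not match three collections. Reordering also needs time before the infusion, or an allocation or disclosure step during it. These points limit the weight of the concern without answering it.

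**Conclusion.** The concern holds on both parts, and the plan should be changed.

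The order in section 9 puts randomisation before the baseline scales, and nothing in the documents keeps the arm from the participant until they are done. The size of any resulting bias is unknown because the documents give no basis for d or k. In the scenarios shown, the planned test's false-positive rate runs from 5% (no shift, or full persistence) to 49.1% (d = 0.3, k = 0, ρ = 0.7). No choice of model repairs this.

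The efficiency loss follows algebraically: ANCOVA's variance is (1+ρ)/2 times that of the planned test. At 0.5 SD and 50 per arm the gain in power is 18.5 percentage points at ρ = 0.3, 11.8 at 0.5, 4.0 at 0.7 and 0.9 at 0.8. This assumes 1:1 allocation, equal SDs and an unaffected baseline. Reading the condition main effect as the efficacy result would be much worse, with power of 26.1% to 34.1% over the same range.

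**What to change.** **Timing.** State in section 9 that the distress VAS, CD-RISC and FACIT-G are completed and saved in REDCap after consent and before randomisation, or at least before the arm is disclosed and the packet handed over. State the point of disclosure. This is compatible with section 30.

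**Analysis.** In section 11, item 3, name ANCOVA (final score on arm and baseline score) as the between-arm test for each scale. State that neither the condition main effect nor a within-arm paired test is evidence of efficacy. Say which forms the paired-test sentence in section 11 covers. Do not present ANCOVA as a correction for the timing.

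**If enrolment is complete.** Specify ANCOVA before the data are examined, on grounds of precision only; report the change-score result as a sensitivity analysis; and state the baseline timing as a limitation. Neither model can be preferred on grounds of bias, because k is unknown.

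**Cost.** No extra patients, visits, forms or software: the same questionnaires on the same day, already entered directly in REDCap. The practical burden is fitting them in before the infusion, or holding back allocation or disclosure until they are saved. The analysis change is a few lines of text.
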